Mechanisms of immune evasion in SCCHN and other cancer types include tumor cell adaptation, direct T-cell suppression via inhibitory cell surface receptors or soluble factors, decreased immune stimulation, and the recruitment of immuno-suppressive cell populations (Horton et al 2019, Kok 2020).

For patients with R/M SCCHN who have progressed on anti-PD-1 therapy, there are limited therapeutic options. Those who progressed on or after PD-1 plus chemotherapy may be treated with single-agent chemotherapy, cetuximab, or other experimental therapies. Those whose disease progresses on PD-1 monotherapy may be eligible for treatment with platinum-based chemotherapy regimens or single-agent platinum chemotherapy, other single-agent chemotherapies, cetuximab, or other experimental treatments (NCCN 2020).

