8.3.1. Adverse Events

Adverse events will be monitored from the time the participant signs the ICF until at least 90 days after the last dose of study treatment regardless of the start of a new anticancer therapy. Adverse events for randomized participants that begin or worsen after informed consent should be recorded on the Adverse Events Form in the eCRF regardless of the assumption of a causal relationship with the study treatment. Conditions that were already present at the time of informed consent should be recorded on the Medical History Form in the eCRF. Adverse events (including laboratory abnormalities that constitute AEs) should be described using a diagnosis whenever possible rather than by individual underlying signs and symptoms.

Adverse events will be reported by the participant (or, when appropriate, by a caregiver, surrogate). The investigator and any qualified designees are responsible for detecting, documenting, and recording events that meet the definition of an AE or SAE and remain responsible for following-up on AEs that are serious, considered related to the study treatment/procedures, or that caused the participant to discontinue the study treatment. Care will be taken not to introduce bias when detecting AEs and/or SAEs. Open-ended and nonleading verbal questioning of the participant, such as "How are you feeling?" is the preferred method to inquire about AE occurrences. Adverse events may also be detected when they are volunteered by the participant during the screening process or between visits or through physical examinations, laboratory tests, or other assessments. The definition, reporting, and recording requirements for AEs are described in Section 9.

All SAEs will be reported to the sponsor or designee within 24 hours. The investigator will submit any updated SAE data to the sponsor within 24 hours of it being available.

After the initial AE/SAE report, the investigator is required to proactively follow each participant at subsequent visits/contacts. All SAEs will be followed until resolution, stabilization, the event is otherwise explained, or the participant is lost to follow-up (as defined in Section 7.3).

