8.8. Follow-Up

8.8.1. Safety Follow-Up

The safety follow-up period starts once the participant discontinues study treatment. Approximately 30 days (± 7 days) and 90 days (± 7 days) after the EOT, participants are to attend a clinic visit for safety evaluation. Adverse events and SAEs must be reported up until 1) at least 90 days after the last dose of study treatment regardless of the start of a new anticancer therapy or 2) until toxicities resolve, return to baseline, or are deemed irreversible, whichever is longer.

Reasonable efforts should be made to have the participant return for the follow-up visits and report any AEs that may occur during this period. If the participant cannot return to the site for the safety follow-up visit, the participant should be contacted by telephone or other methods of communication for assessment of any AEs; this contact should be documented in the source.

If a participant is scheduled to begin a new anticancer therapy before the planned 30-day safety follow-up visit, the safety follow-up visit should be performed before a new anticancer therapy is started. Once a new anticancer therapy has been initiated, the participant will move into the survival follow-up period.

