3. STUDY DESIGN

This is a randomized, double-blind, controlled Phase 2 study to evaluate the efficacy and safety of the combination of retifanlimab plus INCAGN02385 and retifanlimab plus INCAGN02385 and INCAGN02390 compared with retifanlimab alone as first-line treatment in participants with PD-L1–positive, systemic therapy–naïve R/M SCCHN.

Approximately 162 participants will be randomized in a 1:1:1 ratio (approximately 54 participants per group) to 1 of the following treatment groups:

[figure not shown]
- TG1: retifanlimab plus placebo (INCAGN02385) and placebo (INCAGN02390)
- TG2: retifanlimab plus INCAGN02385 and placebo (INCAGN02390)
- TG3: retifanlimab plus INCAGN02385 and INCAGN02390

At randomization, participants will be stratified based on the following factors:

- LAG-3 expression status (determined centrally): positive ($\geq 5\%$) versus negative ($< 5\%$)
- PD-L1 CPS (determined centrally): 1%-19% versus $\geq 20\%$
- HPV p16 status (oropharyngeal only): p16-positive versus p16-negative;
HPV p16 status for participants without oropharynx cancer (eg, cancers of the oral cavity, hypopharynx, larynx) is considered HPV p16-negative.

The study design schema is shown in [Figure 1](#).

Figure 1: Study Design Schema

The study will include a 28-day screening period to determine eligibility, a treatment period in 4-week cycles for up to 2 years or until discontinuation criteria are met, an end-of-treatment visit, and 30-day and 90-day safety follow-up visits. Tumor assessments will be performed at baseline and subsequently Q8W for the first year of treatment and Q12W thereafter by site investigator review according to RECIST v1.1. Safety will be evaluated from the time the participant signs the informed consent form until the 90-day safety follow-up regardless of the start of a new anticancer therapy. Study treatment will begin on Day 1.

After 30 participants have been randomized and have received treatment for at least 4 weeks (at least 2 doses), an interim analysis of safety will be performed by an independent, external DSMB. Additional DSMB review of unblinded safety data will occur per the DSMB charter.

Details of the study design are in Section 4 of the Protocol.

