8.2. Adverse Events

8.2.1. Adverse Event Definitions

All safety analyses will be conducted using the safety population.

A TEAE is any AE either reported for the first time, or worsening of a pre-existing event, after first dose of study drug until 90 days after the last dose of study drug. Analysis of AEs (as discussed below) will be limited to TEAEs, but data listings will include all AEs regardless of their timing in relation to study drug administration, flagging those that are not TEAE. For purposes of analysis, all AEs will be considered TEAEs unless the AE can unequivocally be defined as not treatment-emergent.

Adverse events will be tabulated by MedDRA SOC and PT. Severity of AEs will be graded using the NCI CTCAE v5.0 using Grades 1 through 5. The CTCAE reporting guidelines and grading details are available on the Cancer Therapy Evaluation Program website.

The subset of AEs considered by the investigator to be related to study drug will be considered to be treatment-related AEs. If the investigator does not specify the relationship of the AE to study drug, the AE will be considered to be treatment-related. The incidence of AEs and treatment-related AEs will be tabulated. In addition, serious TEAEs will also be tabulated

Any missing onset date, causality, or severity must be queried for resolution. Unresolved missing or partial dates will be handled using the rules described in Section 4.1.4. Unresolved missing causality and severity will be handled according to the following rules:

- An unresolved missing causality will be considered treatment-related.
- An unresolved missing severity will be identified as an unknown severity.

The number and percentage (%) of participants reporting any TEAEs, any serious TEAEs, any Grade 3 or higher TEAEs, any treatment-related TEAEs, any treatment-related serious TEAEs, any treatment-related Grade 3 or higher TEAEs, any fatal TEAEs, and any TEAEs leading to treatment interruption/discontinuation will be tabulated by MedDRA SOC and PT. Data listings will include all AEs regardless of their timing to study drug administration.

Infusion-related reactions, as well as irAEs, may be summarized separately.

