8.2.2. Adverse Events of Special Interest

Adverse events of special interest will include irAEs and IRRs; these events will be coded according to MedDRA along with all other AEs.

Immune-related AEs will be using the sponsor-predefined PTs based on the immune checkpoint inhibitor class regardless of the investigator's assessment of causality. The sponsor-assessed irAEs will be summarized by grouped term, PT, and severity grade (ie, CTCAE Grades 1, 2, 3, 4, 5).

Infusion-related reactions will be identified using sponsor-predefined PTs indicating a diagnosis of IRRs or symptoms potentially associated with IRRs. Diagnosis of infusion reaction occurring anytime of the treatment period, or symptom of infusion reaction that occurred within 1 day of infusion, and resolved within 2 days from AE onset, are captured as infusion reactions. The sponsor-assessed IRRs will be summarized by grouped term, PT, and severity grade (ie, CTCAE Grades 1, 2, 3, 4, 5).

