10.2. Changes to the Statistical Analysis Plan

The following updates were made for SAP Amendment 1:

- Removed Type I error control. This is not a registrational study and the Type I error was used only for the purpose of sample size calculation, not for any decision making.
- Updated the timing of final analysis, which is to occur when either the required number of PFS events has been observed or the last participant had been followed for a minimum of 8 months after randomization, whichever is earlier.
- Updated Table 6 to align with the Protocol. One sensitivity analysis was kept for the interests of the study.
- Added analysis for median PFS follow-up time.
- Added the number of target lesions for subgroup analysis.
- Updated the OS analysis to only provide estimates of median OS and landmark estimates, its 95% CI, median follow-up time for OS, and HR. The number of OS events at the final analysis does not support a valid comparison between treatment groups, and the study is not powered for OS comparison. No formal statistical testing will be conducted.
- Revised the planned tables.

The following updates were made for SAP Amendment 2:

- Removed summary of prior radiotherapy and surgery, as listings are adequate for reporting.
- Updated efficacy hypothesis description to align with the Protocol.
- Updated ORR and DCR analysis to show only the differences in ORR or DCR between treatment groups and the corresponding 95% CI. Common risk difference and the corresponding 95% CI was added to consider weighted average of differences according to the strata. Odds ratio and 95% CI will not be provided, as the differences are more easily interpretable.
- HPV p16 status for participants without oropharyngeal cancer in the primary PFS analysis will be considered HPV p16-negative, aligning with the strata used for randomization. However, in the sensitivity analysis with actual stratification factors and subgroup analysis, HPV p16 status for participants without oropharyngeal cancer will be marked as not applicable in the subgroup analysis.
- Clarified the subgroup analysis based on number of target lesions will be applicable for PFS analysis only.

- Removed the investigator-assessed irAE summary, as the sponsor-assessed irAE data will suffice for safety evaluation.
- Revised the overall summary of AEs to align with the required analysis.
- Revised the planned tables.

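### The TEAE and irAE tables run to 90 days after last dose with no version that stops at new anticancer therapy, so next-line toxicity can enter the all-causality comparisons and pull the groups together

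*SAP*

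**What the plan says.** SAP 8.2.1 defines a TEAE as a new or worsened AE arising "after first dose of study drug until 90 days after the last dose of study drug". Doubtful cases default to inclusion: "all AEs will be considered TEAEs unless the AE can unequivocally be defined as not treatment-emergent". Neither rule refers to new anticancer therapy.

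Collection matches that window. Protocol 8.3.1 monitors AEs "until at least 90 days after the last dose of study treatment regardless of the start of a new anticancer therapy", and SAP 3 evaluates safety "until the 90-day safety follow-up regardless of the start of a new anticancer therapy".

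SAP 8.2.2 identifies irAEs from sponsor-predefined preferred terms "based on the immune checkpoint inhibitor class regardless of the investigator's assessment of causality". SAP 10.2 records, for Amendment 2: "Removed the investigator-assessed irAE summary, as the sponsor-assessed irAE data will suffice for safety evaluation". In Appendix A the investigator-assessed irAEs survive only as Listing 2.7.8.1, and no planned table separates events before and after new therapy.

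On what follows progression, Protocol 2.1.2 says: "Those whose disease progresses on PD-1 monotherapy may be eligible for treatment with platinum-based chemotherapy regimens". It also names other single-agent chemotherapy and cetuximab. Protocol 8.8.1 allows for new therapy starting before the 30-day safety visit, and adds: "Once a new anticancer therapy has been initiated, the participant will move into the survival follow-up period".

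**The concern.** A secondary objective is the safety of TG2 and TG3 compared with TG1. With an assumed TG1 median PFS of 3 months, most participants will stop treatment for progression, and many may start chemotherapy or cetuximab while the 90-day window is still open. Events caused by that therapy meet the TEAE definition and, where the preferred term is on the sponsor's list, the irAE definition too.

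This adds a background unrelated to the randomised drugs. A similar background in every group shrinks a true difference. It is also likely to be somewhat larger in TG1, where more participants will have progressed by the cutoff, and that shrinks the difference further.

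The SAP already treats new therapy as a break point for efficacy: the primary PFS analysis censors before it (Table 6), and best overall response ignores later assessments (7.4.1). The between-group safety tables have no counterpart.

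**Working it through.** **Design inputs.** HR 0.6, 1-sided alpha 5%, 94 events in two groups, about 54 per group, month-20 analysis (SAP 3 and 3.2). TG1 median PFS 3 months, 12-month enrolment (Protocol Table 17). Under exponential PFS the combination median is 3/0.6 = 5 months.

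**The plan's own figure.** Schoenfeld: 4 × (1.645 + 0.842)² / (ln 0.6)² = 94.8 events. With 94 events power is 0.797 at alpha 5% and 0.884 at 10%, against 0.8000 and 0.8840 in SAP Table 2. The design is reproduced.

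**Share with a PFS event by month 20.** With uniform accrual, follow-up runs from 8 to 20 months. Let λ = ln 2 / median, and let s be the share with an event:

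s = 1 − (e^(−8λ) − e^(−20λ)) / (12λ)

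- TG1: λ = 0.2310, s = 94.7%
- Combination: λ = 0.1386, s = 83.9%

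Check: 54 × (0.947 + 0.839) = 96 events, close to the planned 94.

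**Share of TEAE at-risk time after treatment.** Assume treatment stops at the PFS event and ignore the 1% annual dropout. Let W = 90/30.4375 = 2.96 months.

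- Mean time on treatment = s/λ: 4.10 months (TG1), 6.05 months (combination).
- Mean post-treatment window before cutoff = W − (1 − s)(e^(λW) − 1)/λ: 2.73 and 2.37 months.
- Share: 2.73/6.83 = 40% in TG1; 2.37/8.42 = 28% in a combination arm.

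**Dilution.** Let p be the true rate without next-line events, q the share of those with a PFS event who start next-line therapy inside the window, and r the chance of a counted event on it:

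observed rate = p + (1 − p) × q × r × s

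The documents give none of p, q or r. Taking p = 20% in TG1 and 35% in a combination arm (difference 15.0 points, ratio 1.75):

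| q | r | TG1 | Combination | Difference | Shrinkage | Ratio |
|---|---|---|---|---|---|---|
| 0.2 | 0.05 | 20.8% | 35.5% | 14.8 | 1% | 1.71 |
| 0.3 | 0.10 | 22.3% | 36.6% | 14.4 | 4% | 1.64 |
| 0.5 | 0.20 | 27.6% | 40.5% | 12.9 | 14% | 1.47 |
| 0.7 | 0.30 | 35.9% | 46.5% | 10.6 | 30% | 1.29 |

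With s = 1 in both groups the difference shrinks by the factor 1 − qr. For the last row that is 15 × 0.79 = 11.85 points, so most of the loss comes from the common background and the rest from unequal s.

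**Against sampling error.** The 95% CI half-width at 54 per group is 1.96 × √((0.20 × 0.80 + 0.35 × 0.65)/54) = 16.6 points. The largest loss in the table is 15.0 − 10.6 = 4.4 points.

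**The case against.** Several limits on the point stand.

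- **Attribution.** A reader might infer that next-line toxicity is counted as study-drug toxicity. The documents do not support that. A TEAE is a category of timing. SAP 8.2.1 and 8.2.3 tabulate treatment-related, related serious and related Grade 3 or higher TEAEs on investigator causality, and relatedness to each drug. An event attributed to next-line therapy drops out of these unless causality stays missing after query. Infusion reactions are tied to the treatment period or to one day from infusion. Tables of events leading to interruption, delay or discontinuation concern study drug only.
- **The irAE list.** It cannot be seen, and an earlier use was narrow. In Protocol 2.2.3, among 40 INCAGN02390 monotherapy participants, diarrhea occurred in 15.0% (6) and pruritus in 17.5% (7). Only 4 had an immune-related TEAE; pruritus counted in 1 and diarrhea is not among the terms reported. The same account does include acute kidney injury and dermatitis, so non-specific terms can qualify.
- **Size.** Inputs can be chosen to look alarming. True rates of 5% and 15%, with q = 0.6 and r = 0.30, are reported as about 21% and 28%, so a ratio of 3.0 becomes 1.3. Nothing in the documents supports those inputs. The difference moves from 10 to 6.6 points, against a half-width of about 11.
- **Model.** PFS events include deaths, after which no therapy can start, and Protocol 6.5.5 lets treatment continue while progression is confirmed. Both argue against the upper end of q.
- **Purpose.** The 90-day window is deliberate. Protocol 6.5.3 ties it to late-onset immune toxicity. Truncating the main tables would lose late irAEs and, under this model, shorten observation more in TG1.
- **Collection rule.** A reader might see Protocol 8.8.1 as contradicting itself. It requires at least 90 days of reporting regardless of new therapy, 7.1.2 follows each participant for 90 days, and 8.8.3 moves participants to survival follow-up after the last dose in any case, so the two periods overlap. What remains is unclear wording: Table 3 marks no AE assessment under survival follow-up.

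None of this supplies a between-group table free of next-line events for the all-causality and sponsor-assessed irAE comparisons.

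**Conclusion.** The point holds for the all-causality TEAE, serious, Grade 3 or higher, fatal and sponsor-assessed irAE tables. These can mix events on next-line therapy with events on study treatment, and the plan has no summary that separates them. Under the model the effect pulls the groups together. It shrinks a 15-point difference by about 1% to 30% over the assumed range. This rests on exponential PFS at the design medians, treatment ending at the PFS event, and values of p, q and r that the documents do not give. The loss is smaller than sampling error at 54 per group throughout that range, but it is systematic, so it warrants an added analysis rather than a replacement of the 90-day window.

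The removal of the investigator-assessed irAE summary, against Protocol 9.5, which plans both versions, is a separate discrepancy that truncated tables would not settle.

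**What to change.** - Keep the full 90-day TEAE and irAE tables as planned.
- In SAP 8.2.1 and 8.2.3, add between-group tables of TEAEs (including Grade 3 or higher and serious) and of sponsor-assessed irAEs. End them at the earlier of 90 days after last dose and the day before the first new systemic anticancer therapy.
- In the AE listings, flag events that start on or after new therapy.
- Reconcile Protocol 8.8.1, 8.8.3 and Table 3 so that moving to survival follow-up is not read as ending the 90-day AE collection.

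The cost is a few extra tables and one derived flag. The therapy dates are already needed for PFS censoring, and post-treatment therapy is already summarised (Table 1.4.7). The downside is that the truncated tables omit late irAEs first appearing after new therapy and shorten observation unequally, so both versions must be read together.

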8.2.2. Adverse Events of Special Interest

Adverse events of special interest will include irAEs and IRRs; these events will be coded according to MedDRA along with all other AEs.

Immune-related AEs will be using the sponsor-predefined PTs based on the immune checkpoint inhibitor class regardless of the investigator's assessment of causality. The sponsor-assessed irAEs will be summarized by grouped term, PT, and severity grade (ie, CTCAE Grades 1, 2, 3, 4, 5).

Infusion-related reactions will be identified using sponsor-predefined PTs indicating a diagnosis of IRRs or symptoms potentially associated with IRRs. Diagnosis of infusion reaction occurring anytime of the treatment period, or symptom of infusion reaction that occurred within 1 day of infusion, and resolved within 2 days from AE onset, are captured as infusion reactions. The sponsor-assessed IRRs will be summarized by grouped term, PT, and severity grade (ie, CTCAE Grades 1, 2, 3, 4, 5).

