Two participants (11.8%) had TEAEs leading to discontinuation of study drug, which included pericardial effusion, myocarditis, and pneumonitis.

No fatal TEAEs were reported after administration of INCAGN02385 in combination with INCAGN02390 and retifanlimab.

Immune-related AEs were identified using sponsor-predefined preferred terms based on the ICI class regardless of investigator's assessment of causality. Two participants (11.8%) had at least 1 immune-related TEAE, which included myocarditis, pruritus, and pneumonitis in 1 participant (5.9%) each. All immune-related reactions were assessed as related to study treatment.

Infusion-related reactions included sponsor-predefined preferred terms indicating a diagnosis of IRRs or symptoms potentially associated with IRRs. Four participants (23.5%) had at least 1 infusion-related TEAE, which included pyrexia and IRR in 2 participants (11.8%) each and chills in 1 participant (5.9%). Two of these participants had infusion-related TEAEs considered related to study treatment, which was pyrexia in both participants. Chills was considered to not be related to study treatment by the investigator, and both events of IRR were considered related only to INCAGN02385. All infusion-related TEAEs were nonserious and Grades 1 or 2 in severity.

There were no DLTs in Study INCAGN 2385-201. Enrollment in Phase 1, Part 2 of Study INCAGN 2385-201 has been completed.

Overall, the preliminary toxicity profiles of the combination regimens, including the triplet combination of INCAGN02385, INCAGN02390, and retifanlimab, were consistent with those anticipated with checkpoints blockade with no safety signals based on those preliminary data.

More detailed information about the known and expected benefits and risks and reasonably expected AEs of the study drugs retifanlimab, INCAGN02385, and INCAGN02390 may be found in the respective IBs ([retifanlimab IB](#), [INCAGN02385 IB](#), [INCAGN02390 IB](#)).

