9.5. Events of Clinical Interest

No specific AEs are expected to be sent to the sponsor within an expedited manner aside from the AEs that meet the seriousness category as described in Section 9.4.

Immune-related AEs will be identified by investigator assessment as well as using sponsor-predefined preferred terms based on the ICI class regardless of investigator's assessment of causality. Both investigator assessed and sponsor-assessed irAEs will be summarized.

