10.4.4. Safety Analyses

Safety analyses will be conducted for the safety population.

All TEAEs, clinical laboratory measurements, vital sign measurements, and ECG values will be summarized by treatment group. Quantitative safety variables and their changes from baseline (laboratory, vital signs, and ECG values) will be summarized with descriptive statistics. Abnormal values outside of established ranges will be flagged and tabulated based on predefined criteria.

Measures of exposure (eg, days of exposure, dose modification, dose intensity) of study drug will be summarized descriptively.

[figure not shown]
Adverse events will be coded by the MedDRA dictionary and severity of AEs will be based on the NCI CTCAE v5.0 using Grades 1 through 5. A TEAE is defined as an AE either reported for the first time or worsening of a pre-existing event after first dose of study drug and within 90 days of the last dose. The number and percentage (%) of participants reporting any TEAEs, any serious TEAEs, any Grade 3 or higher TEAEs, any treatment-related TEAEs, any treatment-related serious TEAEs, any treatment-related Grade 3 or higher TEAEs, any fatal TEAEs, and any TEAEs leading to treatment interruption/discontinuation will be tabulated by MedDRA system organ class and preferred term. Data listings will include all AEs regardless of their timing to study drug administration. Adverse events of clinical interest will be summarized as detailed in the SAP.

The clinical laboratory data will be analyzed using summary statistics; no formal treatment group comparisons are planned. In addition, distributions of key laboratory parameters may be plotted over time; these values will also be classified into CTCAE toxicity grades when applicable and tabulated.

[figure not shown]
Descriptive statistics and mean change from baseline will be determined for vital signs at each assessment time. The abnormal values for participants exhibiting vital sign abnormalities will be listed.

The abnormal values for participants exhibiting ECG abnormalities will be listed.

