3.5.4	Summary of QTcB Interval (ms) From 12-Lead ECG	Safety	X	
3.5.5	Summary of QTcF Interval (ms) From 12-Lead ECG	Safety	X	
3.5.7	Summary of Heart Rate (bpm) From 12-Lead ECG	Safety	X	
3.5.8	Summary of Outliers of QT and QTcB and QTcF Interval Values From 12-Lead ECG	Safety	X	
3.5.9	Summary of Clinically Significant ECG Abnormality	Safety	X	

Figures

Figure No.	Title	DSMB
1.1	Kaplan-Meier Estimates of Progression-Free Survival by RECIST	
1.2	Forest Plot of Progression-Free Survival-TG2 vs TG1 by Subgroup	
1.3	Forest Plot of Progression-Free Survival-TG3 vs TG1 by Subgroup	
2.1	Kaplan-Meier Estimates of Duration of Response by RECIST	
2.2	Kaplan-Meier Estimates of Overall Survival	
3.1	Spider Plot of Percent Change from Baseline in Sum of Target Lesions	
3.2	Waterfall Plot of Best Percentage Change in Sum of Target Lesions	
3.3	Swimmer Plot of Overall Response and Duration of Treatment	
4.1	Line Graph of Selected Laboratory Values by Study Visit	X

Listings

Listing No.	Title	DSMB
2.1.1	Participant Enrollment and Disposition Status	X
2.2.1	Protocol Deviations	
2.2.2	Participant Inclusion and Exclusion Criteria Violations	
2.3.1	Analysis Populations	X
2.4.1	Demographic and Baseline Characteristics	X
2.4.2	Baseline Disease Characteristics and Disease History	X

Listing No.	Title	DSMB
2.4.3	Prior Radiation Treatment	
2.4.4	Prior Systemic Therapy	
2.4.5	Prior Surgery or Surgical Procedure	
2.4.7	Medical History	
2.4.8	Prior and Concomitant Medication	
2.5.1	Procedures and Nondrug Therapy	
2.5.2	Study Drug Administration	X
2.6.1	Deaths	
2.6.2	Best Overall Response, Duration of Response, and Progression-Free Survival	
2.6.3	Largest Percentage Reduction in Sum of Diameters of Target Lesions	
2.6.4	Overall Response Assessment by Visit	
2.6.5	Response Assessment: Target Lesions	
2.6.6	Response Assessment: Nontarget Lesions	
2.6.7	Response Assessment: New Lesions	
2.6.8	ECOG Status	
2.7.2	Adverse Events	X
2.7.3	Adverse Events Grade ≥ 3	X
2.7.4	Serious Adverse Events	X
2.7.5	Fatal Adverse Events	X
2.7.7.1	Adverse Events Leading to Interruption or Discontinuation of Study Drug	X
2.7.8.1	Immune-Related Adverse Events (Investigator-Assessed)	
2.7.8.2	Immune-Related Adverse Events (Sponsor-Assessed)	X
2.7.9.1	Infusion-Related Adverse Events (Sponsor-Assessed)	X
2.8.1	Clinical Laboratory Values - Hematology	X
2.8.2	Clinical Laboratory Values - Chemistry	X
2.8.3	Clinical Laboratory Values - Coagulation	
2.8.4	Clinical Laboratory Values - Urinalysis	

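### The SAP drops the summary of investigator-assessed irAEs that Protocol 9.5 requires, and SAP 10.1 does not record the departure

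*SAP*

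**What the plan says.** Protocol 9.5 sets out how irAEs are found: "Immune-related AEs will be identified by investigator assessment as well as using sponsor-predefined preferred terms based on the ICI class". It then commits to the output: "Both investigator assessed and sponsor-assessed irAEs will be summarized". Protocol 10.4.4 leaves the detail to the SAP: "Adverse events of clinical interest will be summarized as detailed in the SAP".

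SAP 2.1 states that the SAP rests on Protocol Amendment 2, which contains this text. SAP 8.2.2 nevertheless gives a single route: "Immune-related AEs will be using the sponsor-predefined PTs based on the immune checkpoint inhibitor class regardless of the investigator's assessment of causality". The sentence has lost its verb, but the meaning is clear. The output follows suit: "The sponsor-assessed irAEs will be summarized by grouped term, PT, and severity grade".

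SAP 10.2, under Amendment 2, records that the investigator-assessed irAE summary was taken out because the sponsor-assessed data were considered enough. SAP 10.1, which lists changes to Protocol-defined analyses, has an entry for Amendment 2 that covers only ORR and DCR.

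**The concern.** The safety of TG2 and TG3 compared with TG1 is a secondary objective, and irAEs are one of the two categories of special interest in SAP 8.2.2. The two ways of finding an irAE measure different things. Protocol 6.5.3 describes an irAE clinically: cause unknown, associated with drug exposure, consistent with an immune mechanism, and labelled only after efforts to rule out other causes. The sponsor list works by preferred term and ignores the investigator's view of causality. Agreement between the two is therefore an empirical question, and the planned tables would not answer it.

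Without the investigator-assessed summary, the report has no by-arm count of the events that the treating physicians judged immune-related. The clinical study report would also depart from a Protocol statement without saying so where a reader would look for it.

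**Working it through.** The plan states no figure to reproduce here. The check is a comparison of texts and a count of outputs, followed by two short calculations.

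**1. Planned irAE outputs by source of assessment**

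| Output | Sponsor-assessed | Investigator-assessed |
|---|---|---|
| Rows in the overall AE summary (SAP 8.2.3) | 1 | 0 |
| Summaries by term (SAP 8.2.3) | 3 | 0 |
| Appendix A tables (3.2.17.1 to 3.2.17.3) | 3, all marked for the DSMB | 0 |
| Appendix A listings | 1 (2.7.8.2, marked for the DSMB) | 1 (2.7.8.1, not marked) |

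An off-list event that an investigator calls immune-related is thus counted in none of the irAE tables. SAP 8.2.1 adds that irAEs may be summarized separately, but that wording is optional and names no source.

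**2. Where the change is logged.** The Amendment 2 change to ORR and DCR appears in both SAP 10.1 and SAP 10.2. The irAE removal appears only in 10.2. By the SAP's own practice, a change to something the Protocol specifies belongs in both.

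**3. Can the sponsor list stand in for the investigator's assessment?** Two items in the Protocol bear on this.

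- Protocol 2.2.4, doublet of INCAGN02385 and INCAGN02390: pancreatitis was counted as an immune-related TEAE although it was judged unrelated to study treatment. The sponsor approach can therefore count events that an investigator would not. The documents give no clear example of the reverse.
- Protocol 2.2.3, INCAGN02390 monotherapy: pruritus was reported in 17.5% of 40 participants, and 0.175 × 40 = 7. Pruritus as an immune-related TEAE is given for 1 participant. Only 4 participants had any immune-related TEAE, so at least 7 − 4 = 3 participants with pruritus were not counted at all. This suggests that identification in that study was not a plain match on preferred term. SAP 8.2.2 gives a timing rule for infusion reactions but no further rule for irAEs.

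**4. Size per participant.** Take about 54 participants per arm (Protocol 4.2), and assume all are treated so that the safety denominator is also 54. If *d* participants in an arm have an off-list irAE and no listed one, the reported incidence omits *d*/54:

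- *d* = 1: 1/54 = 1.9 percentage points
- *d* = 2: 2/54 = 3.7 points
- *d* = 3: 3/54 = 5.6 points

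For scale, the earlier triplet cohort had 2/17 = 11.8% with a sponsor-assessed irAE. The effect on a between-arm difference is (*d* in TG2 or TG3 − *d* in TG1)/54. It can take either sign, and the documents give no value for either term.

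**The case against.** The best defence is that the change was deliberate, disclosed with a reason in SAP 10.2, and made under a Protocol that hands the detail to the SAP. Protocol 10 promises an amendment for changes to hypotheses and their methods, and no hypothesis attaches to AEs. The events also stay in view. They appear by arm in the TEAE tables and, where they qualify, in the Grade 3 or higher, serious, treatment-related and discontinuation tables, most of which go to the DSMB. The DSMB also receives the full AE, Grade 3 or higher and serious AE listings.

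Most of this stands, and it limits the consequence. It does not remove the conflict. Leaving detail to the SAP does not cancel an explicit statement that both sets will be summarized, and a general TEAE table does not show which events were judged immune-related.

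Two stronger readings are tempting, and the documents support neither.

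- *A reader might infer that immune toxicity in TG2 and TG3 is understated relative to TG1*, because the list follows a drug class and those arms add newer targets. But the list is not in the documents, and the Protocol's background section itself treats LAG-3 and TIM-3 as checkpoint pathways. The same approach picked up vasculitis and pancreatitis in the doublet without retifanlimab. All three arms receive retifanlimab and investigators are blinded, so off-list irAEs can be recorded in any arm.
- *A reader might take the pericardial effusion in the earlier triplet cohort as a missed irAE.* It was serious and led to discontinuation, while two participants had irAEs, "which included myocarditis, pruritus, and pneumonitis in 1 participant (5.9%) each". Nothing says that an investigator judged the effusion immune-related. Two participants discontinued, with effusion, myocarditis and pneumonitis between them. If myocarditis and pneumonitis fell in different people, those two were both the discontinuers and the irAE cases, so the effusion was in someone already counted. If they fell in the same person, the effusion could be elsewhere. The Protocol does not say which.

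**Conclusion.** The point holds as a conflict between the current Protocol and the current SAP. Protocol 9.5 requires two irAE summaries, the SAP plans one, and SAP 10.1 does not record the departure. The practical result is that no by-arm irAE table counts an investigator-assessed event outside the sponsor list.

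The only size that can be stated is conditional: about 1.9 percentage points of an arm's irAE incidence for each participant whose sole irAE is off-list, assuming 54 treated per arm. How many such participants there will be, and in which arms, is unknown. The finding is one of incomplete reporting against the Protocol. It does not show bias in the safety comparison, and the events are not lost from the report. It is worth correcting because the safety comparison is a secondary objective and the correction is cheap.

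**What to change.** In SAP 8.2.3 and Appendix A, restore a by-arm table of investigator-assessed irAEs by preferred term and maximum grade, and add a matching investigator-assessed row to Table 3.2.1. The source is the data already needed for Listing 2.7.8.1, so the cost is one table and one row of programming, with no new data collection.

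If the sponsor prefers to keep the removal, amend Protocol 9.5 to match and enter the change, with its reason, in SAP 10.1.

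In either case, complete the defective sentence in SAP 8.2.2, state the full rule by which the sponsor identifies irAEs, and fix the term list before unblinding.

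Two additions would help but are not required by Protocol 9.5: a row counting participants with an irAE by either definition, and DSMB marks for the investigator-assessed outputs.
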